1.3 Study Rationale

Razuprotafib represents a unique, first-in-class, host-targeted intervention to ameliorate progression of pulmonary and vascular pathology in COVID-19, potentially meeting an urgent unmet medical need. A Phase 2 clinical study (RESCUE) has been designed to test the safety and efficacy of SC administration of razuprotafib to reduce the severity of pulmonary and vascular pathology in patients with moderate to severe COVID-19. This would likely result in earlier recovery, fewer patients requiring mechanical ventilation, decreased time in the ICU on ventilator support, and concomitant reduction in morbidity and mortality. Additionally, razuprotafib together with emerging antiviral drugs and other therapeutics could provide the optimal combination of host and virus targeted therapy for the treatment of COVID-19.

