3.4 Efficacy Assessment

All efficacy analysis will be performed using the ITT Population. Selected endpoints will be repeated on the FA and PP Populations. In addition, the efficacy analyses will be analyzed for pooled razuprotafib doses and placebo.

Additional analyses to understand safety and efficacy variables further may be carried out and will be labeled as post-hoc analyses.

3.4.1 *Efficacy Endpoints*

The following parameters will be analyzed using Cochran-Mantel-Haenszel (CMH) test stratified by disease severity:

- Proportion of subjects alive and free of respiratory failure at Day 28;
- Proportion of subjects alive and free of respiratory failure at Day 7;

All results will be summarized descriptively by treatment arm and expressed as proportions, along with corresponding 95% CI of the difference between response rates, and p-values. The 95% CI will be constructed using the normal approximation method.

Additional Analysis may be considered by incorporating other covariate adjustments into the analysis.

Respiratory failure will be defined as subjects who are on invasive mechanical ventilation; are receiving oxygen delivered by high-flow nasal cannula (heated, humidified, oxygen delivered via reinforced nasal cannula at flow rates >20 L/min with fraction of delivered oxygen ≥ 0.5) noninvasive positive pressure ventilation or extracorporeal membrane oxygenation; or have a

clinical diagnosis of respiratory failure (ie, clinical need for 1 of the preceding therapies, but preceding therapies not able to be administered in setting of resource limitation). Subject who die prior to the study timepoint (Day 7 or Day 28) will be imputed based on the worst outcome. Other missing responses will be imputed using a multiple imputation (MI) method under the assumption of missing at random (MAR).

Sensitivity Analysis

- All missing responses will be considered as non-responders and which will be imputed taking the worst case approach.
- The analysis will be repeated on FA and PP Populations.

The following parameters will be analyzed using the CMH test as stated above:

- Proportion of subjects alive and not requiring invasive mechanical ventilation at any time through Day 28;
- Proportion of subjects who improve by ≥ 2 categories on the NIAID 8-point ordinal scale from baseline to Day 7 and baseline to Day 28;
- Proportion of subjects who worsen by ≥ 2 categories on the NIAID 8-point ordinal scale from baseline to Day 7 and baseline to Day 28;

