- All-cause mortality at Day 7 and Day 28; and
- Proportion of subjects who were discharged and remained free of respiratory failure prior to Day 7 and Day 28.

The following parameters will be analyzed using an analysis of variance (ANOVA) model with effects for treatment, baseline value and disease severity as factors:

- Change in $\text{PaO}_2:\text{FiO}_2$ ratio from baseline to Day 7 (or discharge) and baseline to Day 28 (or discharge),
- Length of hospitalization and not requiring invasive mechanical ventilation from baseline to Day 7 and baseline to Day 28 or death,
- Length of hospitalization from baseline to Day 7 and baseline to Day 28 or death,

Missing responses will be imputed using a multiple imputation (MI) method under the assumption of missing at random (MAR).

All results will be summarized descriptively by treatment group, along with corresponding 95% CI of the difference between razuprotafib groups vs. placebo, and p-value.

The length of hospitalization will include all days that the subject is admitted to the hospital. For subjects who are discharged and readmitted to the hospital, the length of hospitalization will include the days after readmission.

Hospitalization days will be counted in 24-hour periods; any partial days will be counted as a whole day.

Days that subjects are on the ventilator will be counted as days of respiratory failure. Days that subjects are of respiratory failure based on the definition will be counted as days of respiratory failure. For subjects receiving high flow oxygen by a nasal cannula or noninvasive positive

pressure ventilation when enrolled, the length of respiratory failure will include all the days of respiratory failure from baseline.

The time-to-event endpoint of time to reach grade 6, 7 or 8 on the NIAID 8-point ordinal scale will be summarized descriptively using the Kaplan-Meier method. The Kaplan-Meier estimate of the median time as well as the 2-sided 95% confidence interval will be presented by treatment group.

The endpoint of number of subjects in each category of the NIAID 8-point ordinal scale at Day 7 and Day 28 will be summarized by treatment group and timepoint using descriptive statistics.

The endpoint of time to return to prehospitalization oxygen requirement will be summarized by treatment group using descriptive statistics.

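### Time to reach NIAID grade 6, 7 or 8 is a named efficacy endpoint, but the SAP plans no between-arm estimate or test for it

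*SAP*

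**What the plan says.** SAP section 2.3.1 lists time to reach grade 6, 7 or 8 among the efficacy endpoints, and section 6 records it as an addition to the protocol. For its analysis, section 3.4.1 says that "time to reach grade 6, 7 or 8 on the NIAID 8-point ordinal scale will be summarized descriptively using the Kaplan-Meier method", and then: "The Kaplan-Meier estimate of the median time as well as the 2-sided 95% confidence interval will be presented by treatment group". Nothing further is planned for it.

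Two related endpoints are treated the same way. On oxygen: "The endpoint of time to return to prehospitalization oxygen requirement will be summarized by treatment group using descriptive statistics". The counts in each NIAID category "will be summarized by treatment group and timepoint using descriptive statistics".

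Other endpoints in section 3.4.1 are compared with placebo. For the binary ones: "The following parameters will be analyzed using Cochran-Mantel-Haenszel (CMH) test stratified by disease severity". For change in PaO2:FiO2 and the two length-of-hospitalization endpoints: "The following parameters will be analyzed using an analysis of variance (ANOVA) model with effects for treatment, baseline value and disease severity as factors". Both groups get a 95% CI for the difference and a p-value.

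Protocol section 1.3 says of the hoped-for reduction in pathology: "This would likely result in earlier recovery, fewer patients requiring mechanical ventilation".

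**The concern.** Efficacy is a primary objective, and speed of recovery is one of the benefits the protocol expects. The sponsor added an endpoint that measures it, yet the planned output does not estimate the treatment effect. Two medians with separate intervals give no interval for the difference or ratio between arms. They also ignore disease severity, by which randomization is stratified (apart from the sentinel subjects). A reader who wants to know whether razuprotafib speeds recovery on this scale would have to compare arm medians by eye.

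The omission is hard to repair later. SAP section 3.4 says that additional analyses will carry a post hoc label, so a contrast left out now loses its prespecified standing.

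**Working it through.** **1. Endpoints side by side (SAP section 3.4.1)**

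| Endpoint type | Analysis | Contrast with placebo |
|---|---|---|
| Binary | CMH, severity-stratified | CI of difference, p-value |
| Three continuous | ANOVA with severity | CI of difference, p-value |
| Time to NIAID grade 6, 7 or 8 | Kaplan-Meier median and CI by arm | none |

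Section 3.1.5 sets two-sided alpha at 0.05 for comparisons but creates none. Section 3.4 adds a pooled-dose analysis, which for this endpoint yields only another arm median.

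**2. What a contrast would deliver**

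The plan has no power figure to reproduce; SAP section 2.2.4 says no formal sample-size assessment was made.

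Inputs from the SAP: 120 subjects in Part 2, so 40 per arm at 1:1:1, and 80 v 40 for pooled doses or 2:1 allocation; two-sided alpha 0.05. Assumptions: placebo recovery by Day 28 of p_c = 60% to 90%, and a constant recovery rate ratio HR.

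Formulas, with π the share of subjects on razuprotafib:
- p_t = 1 − (1 − p_c)^HR
- events d = n_c·p_c + n_t·p_t
- SE(ln HR) = 1/√(d·π(1−π))
- power = Φ(ln HR/SE − 1.96)

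With p_c = 80% and HR = 1.5, p_t = 1 − 0.2^1.5 = 91.1%.
- 40 v 40: d = 32 + 36.4 = 68.4; SE = 1/√(68.4 × 0.25) = 0.242; power = Φ(0.405/0.242 − 1.96) = 39%. An observed ratio of 1.5 would have a 95% CI of 1.5·exp(±1.96 × 0.242), or 0.93 to 2.41.
- 80 v 40: d = 32 + 72.8 = 104.8; SE = 1/√(104.8 × 2/9) = 0.207; power 50%; CI 1.00 to 2.25.

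At HR = 1.8 the powers are 69% and 82%. The ratio detectable with 80% power runs from 2.09 (p_c = 60%) to 1.91 (p_c = 90%) for 40 v 40, and from 1.87 to 1.74 for 80 v 40. For HR = 1.5, 80% power needs (1.96 + 0.84)²/[π(1−π)(ln 1.5)²] events: 191 at 1:1 or 215 at 2:1. Part 2 has 120 subjects.

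**3. Does the plan already test timing?**

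Simulation assumptions:
- half the subjects are moderate
- daily recovery hazards of 0.14 (moderate) and 0.055 (severe)
- daily death hazards of 0.001 and 0.008
- deaths held as not recovered to Day 28

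This gives placebo recovery of 85% by Day 28 and 47% by Day 7. The ANOVA column uses severity-adjusted days to recovery as a stand-in for length of hospitalization, treating recovery as discharge. The CMH columns split the same recovery event at Day 28 and at Day 7; these are not SAP endpoints. Ranges are over repeated runs.

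| Size, ratio | Stratified log-rank | ANOVA on days | CMH Day 28 | CMH Day 7 |
|---|---|---|---|---|
| 80 v 40, 1.75 | 69–71% | 66–69% | 34–36% | 52–53% |
| 80 v 40, 1.5 | 44–45% | 42–43% | 21–25% | 28–30% |
| 40 v 40, 1.75 | 59–60% | 55–56% | 25–27% | 37–41% |

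The log-rank test clearly beats the split outcomes here, but it is only a few points ahead of a days-based ANOVA of the kind already planned.

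**4. Without proportional rates (40 v 40, unstratified simulation)**

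- Only the final share recovering changes (70% v 90%, same speed): log-rank 52%, Day 28 binary 63%.
- Only speed changes (80% recover in both arms, mean 10 v 6 days): log-rank 12%, Day 28 binary 5%, Day 7 binary 28%.

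**The case against.** The best defence is that description is a legitimate choice in a proof-of-concept trial with no formal sample size, and that ANOVA on length of hospitalization already tests speed of recovery. Much of this stands: section 3 of the check shows little power lost under its assumptions, and section 2 shows that a contrast would be imprecise. It does not remove the gap. Length of hospitalization is a different outcome, because a grade 6 subject has reached this endpoint while still in hospital. Limited precision is also a reason to report an interval for the effect.

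A reader might infer four stronger claims, which the documents do not support:
- That every test uses a fixed-day binary outcome. Three continuous endpoints are tested, and one CMH endpoint is cumulative: "Proportion of subjects alive and not requiring invasive mechanical ventilation at any time through Day 28".
- That this is the most informative endpoint. Neither document ranks it.
- That Day 28 outcomes sit near a ceiling. No discharge or recovery rate is given; the 85% above is an assumption.
- That the log-rank test is generally more powerful than the planned tests. The ordering reverses in section 4 of the check, and the documents give no rates for the binary endpoints actually tested.

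**Conclusion.** The concern holds as a gap in the analysis of one named endpoint. Time to NIAID grade 6, 7 or 8 has no planned between-arm estimate or test and makes no use of the severity strata, while the binary and continuous endpoints get both a difference and a p-value. It does not show that the trial would miss a real effect on speed of recovery through its choice of tests.

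The gain from a change is mainly an effect estimate with an interval. At about 40 per arm, 80% power needs a ratio of about 1.9 to 2.1, and at 80 v 40 about 1.7 to 1.9. These figures assume proportional recovery rates and placebo recovery of 60% to 90%, neither of which the documents give. The change is worth making before database lock because it is cheap and a later addition would be labelled post hoc.

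**What to change.** In SAP section 3.4.1, for time to reach grade 6, 7 or 8:
- Add a recovery rate ratio versus placebo with 95% CI and a log-rank test, both stratified by disease severity, for each razuprotafib dose and for the pooled doses.
- Truncate follow-up at Day 28 and keep deaths as not recovered to Day 28, in line with the worst-outcome rule in SAP section 3.1.6. That rule is not yet turned into a censoring rule for this endpoint. State as well how subjects lost to follow-up are censored.
- Keep the Kaplan-Meier medians as description.
- State that the results are supportive.

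The cost is a paragraph of SAP text and a few lines of code, with no new data. The downside is up to three more p-values (two doses and the pooled comparison) at an unadjusted 0.05.

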3 STATISTICAL METHODOLOGY

3.1 General Considerations

3.1.1 *Analysis Day*

Analysis day will be calculated from the date of first dose of study drug. The day of the first dose of study drug will be Day 1, and the day immediately before Day 1 will be Day -1. There will be no Day 0.

3.1.2 *Definition of Baseline*

Baseline is defined as the last measurement prior to the first dose of study drug.

3.1.3 *Visit Windows*

No analysis visit windows will be defined for this study, i.e., the nominal visits /time-points will be used for all statistical summaries/analyses.

3.1.4 *Summary Statistics*

Categorical data will generally be summarized with counts and percentages of subjects. The denominator used for the percentage calculation will be clearly defined. Continuous data will generally be summarized with descriptive statistics including n (number of non-missing values), mean, median, standard deviation, minimum, and maximum.

Summaries of change from baseline variables will include only patients who have both a baseline value and corresponding value at the post-baseline time point of interest.

3.1.5 *Hypothesis Testing*

All statistical comparisons will be made using two-sided tests at $\alpha = 0.05$. All null hypotheses will be of no treatment difference, and all alternative hypotheses will be two-sided. Confidence intervals will be two-sided, unless stated otherwise.

3.1.6 *Handling of Dropouts and Missing Data*

For all efficacy endpoints that do not include death as a possible outcome, data from subjects who die prior to Day 28 will be imputed at Day 28 based on the worst outcome. Other missing data for selected endpoints will be imputed using the methods as described in Section 3.4.

In cases of missing or incomplete dates (e.g. AE and concomitant medications), the missing component(s) will be assumed as the most conservative value possible. For example, AEs with missing start dates, but with stop dates either overlapping into the treatment period or missing,

will be counted as treatment-emergent, taking the worst-case approach. When partial dates are present in the data, both a partial start date and/or a partial stop date will be evaluated to determine whether it can be conclusively established that the AE started prior to the start of study drug or ended prior to the start of study drug. If the above cannot be conclusively established based on the partial and/or present dates, then the AE will be considered as treatment-emergent.

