3.3 Subject Data and Study Conduct

3.3.1 *Subject Disposition*

The number and percentage of subjects in each of the following categories will be presented by the treatment group and overall for all screened subjects:

- screened,
- randomized,
- treated,
- randomized but not treated,
- completed the Treatment Period, and
- completed the study.

Primary reasons for discontinuation of study treatment and primary reasons for early withdrawal from the study will be tabulated.

3.3.2 *Protocol Deviations*

Any major protocol deviation will be documented as described in the protocol deviation plan, and its impact on inclusion in each analysis population for any subject will be specified. The final list of protocol deviations impacting the analysis populations will be reviewed prior to database lock. Counts and percentages of subjects with major protocol deviations by deviation category will be summarized for all randomized subjects.

3.3.3 *Analysis Populations*

Counts and percentages of subjects in each analysis population will be summarized by treatment and in total based on all randomized subjects.

3.3.4 *Demographic and Baseline Characteristics*

The following demographic and baseline characteristics will be summarized:

- Age (years)
- Sex
- Race
- Ethnicity
- COVID-19 severity (moderate or severe)
- NIAID Assessment
- $\text{PaO}_2:\text{FiO}_2$ ratio
- Pre-hospitalization oxygen requirement (None, Low-flow or High-flow Nasal cannula or CPAP mask)
- Concomitant medication to treat COVID-19 at baseline
- Comorbid conditions (diabetes, obesity, hypertension, heart failure, chronic kidney disease)

Demographic and baseline characteristics will be summarized with descriptive statistics or counts and percentages of subjects as appropriate by treatment group and overall for each Analysis Population.

3.3.5 *Medical History*

Medical history will be coded to system organ class and preferred term using the Medical Dictionary for Regulatory Activities (MedDRA) version 23.1. Counts and percentages of subjects with medical history by system organ class and preferred term will be summarized by treatment group and overall.

Counts and percentages of subjects with COVID-19 symptoms will be summarized by treatment group and overall.

3.3.6 *Concomitant Medications*

Concomitant medications will be coded to anatomical therapeutic chemical (ATC) class and preferred term using the World Health Organization Drug Dictionary (WHO Drug Global B3, March 2020).

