7 PROGRAMMING SPECIFICATIONS

Analyses will be performed using SAS® version 9.4 or higher. All available data will be presented in subject data listings which will be sorted by subject and visit date as applicable. Detailed Programming Specifications will be provided in a separate document.

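### Time to return to prehospitalization oxygen requirement has no rule for living subjects who have not returned, and a plain descriptive summary can distort the arm comparison

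*SAP*

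**What the plan says.** SAP 2.3.1 lists 13 efficacy endpoints. Two that measure time to a recovery event are handled differently in SAP 3.4.1:

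- Time to NIAID grade 6, 7 or 8, which the SAP labels a time-to-event endpoint, "will be summarized descriptively using the Kaplan-Meier method", with a median and two-sided 95% confidence interval for each arm.
- "The endpoint of time to return to prehospitalization oxygen requirement will be summarized by treatment group using descriptive statistics". Nothing is said about censoring.

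The general rules that could fill the gap are:

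- SAP 3.1.4: "Continuous data will generally be summarized with descriptive statistics including n (number of non-missing values), mean, median", followed by standard deviation, minimum and maximum.
- SAP 3.1.6, for endpoints that do not already include death: "data from subjects who die prior to Day 28 will be imputed at Day 28 based on the worst outcome".
- SAP 3.1.6, for the rest: "Other missing data for selected endpoints will be imputed using the methods as described in Section 3.4".

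The multiple-imputation sentences in 3.4.1 follow the two respiratory-failure proportions and the ANOVA list. This endpoint is in neither group. SAP 6 (changes from the protocol) does not mention it. SAP 7 adds "Detailed Programming Specifications will be provided in a separate document".

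**The concern.** Follow-up ends at Day 28, so a subject who is alive and still above the prehospital oxygen level then has no observed time. The SAP assigns neither a value nor a censoring time. If the phrase in 3.4.1 carries its 3.1.4 meaning, such subjects count as missing and leave the summary, while subjects who died remain at the worst value. The mean and median then describe only those who returned or died. An arm in which more people fail to recover loses more of its worst results. The reported n would show the loss but would not correct the estimate.

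The endpoint has no planned test, so the descriptive summary is its whole result.

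Two definitions are also open:

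- **Already at the prehospital level.** Protocol 4.1 lets moderate subjects qualify on room air, so some may be at that level at baseline. No rule gives them a time.
- **After discharge.** Oxygen-ratio collection stops (Protocol 3.1.1). Telephone visits cover clinical status, concomitant medications and adverse events (Appendix A, footnote b), and grade 7 of the NIAID scale combines activity limits with home oxygen.

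**Working it through.** **Inputs.** Follow-up of 28 days is from the protocol. Forty per arm is Part 2 at 1:1:1 (120/3). The documents give no return rate, death rate or effect size, so there is no plan figure to reproduce and every rate below is assumed. Setting deaths to 28 days is also an assumption, because the SAP does not state the worst value for a time variable.

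**Medians.** Take a constant return hazard h per day and a share d who die without returning. The proportion of the others returned by Day 28 is F = 1 − exp(−28h).

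- All subjects, with deaths and living non-returners counted as not returned: median = −ln(1 − 0.5/(1−d))/h.
- Living non-returners dropped, deaths at 28: median = −ln(1 − 0.5[(1−d)F + d]/(1−d))/h.

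Example with d = 0, hazards 0.05 vs 0.08:

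- F = 75.3% vs 89.4%, so n would read about 30 vs 36 of 40.
- All subjects: ln2/0.05 = 13.9 and ln2/0.08 = 8.7, difference 5.2 days.
- Dropped: −ln(1 − 0.377)/0.05 = 9.5 and −ln(1 − 0.447)/0.08 = 7.4, difference 2.1 days.

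| Hazards per day | Returned by Day 28 | Difference, dropped | Difference, all subjects |
|---|---|---|---|
| 0.03 vs 0.05 | 56.8% vs 75.3% | 1.7 | 9.2 |
| 0.05 vs 0.08 | 75.3% vs 89.4% | 2.1 | 5.2 |
| 0.10 vs 0.15 | 93.9% vs 98.5% | 1.8 | 2.3 |
| 0.15 vs 0.20 | 98.5% vs 99.6% | 1.1 | 1.2 |

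With 10% deaths in each arm, 0.05 vs 0.08 gives 2.6 against 6.1 days. Over a grid of assumed scenarios (placebo median 7 to 28 days, hazard ratio for return 1.0 to 1.6, deaths 0 to 20%, never-return share 0 to 30%, drug no worse on any), dropping shrank the median difference in all 1,466 cases where both all-subject medians were reached. The median ratio was 0.38.

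**Arms that differ only in the share who return.** Let F(t) = p(1 − exp(−t/8)), with 5% deaths per arm. For p = 60% vs 80%, the dropped medians are 6.0 vs 5.8 and the all-subject medians 14.3 vs 7.8.

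**Means with unequal mortality.** Let h = 0.05 in both arms and deaths be 20% vs 10%. The mean time among returners is 1/h − 28·exp(−28h)/F = 20 − 28(0.2466)/0.7534 = 10.84 days.

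- Returned: 0.8 × 0.7534 = 0.603 and 0.9 × 0.7534 = 0.678.
- Dropped: (0.603×10.84 + 0.2×28)/0.803 = 15.1 and (0.678×10.84 + 0.1×28)/0.778 = 13.0, difference 2.1.
- All non-returners at 28: 0.603×10.84 + 0.397×28 = 17.7 and 0.678×10.84 + 0.322×28 = 16.4, difference 1.3.

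The mean difference widens. The median difference in the same case still shrinks (2.6 against 3.4).

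**Reversal.** Take an arm with p = 60% and 10% deaths. Compare it with the same arm plus 20% who return evenly over Days 14 to 28. The dropped medians are 6.7 vs 10.6, so the better arm looks slower. The all-subject medians are 14.3 vs 14.2; only the Day 28 proportions (58% vs 78%) show the benefit.

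**Informative censoring.** Suppose 10% of each arm are discharged at Day 10 above their prehospital level, do not return by Day 28 and have unknown status. With hazards 0.05 vs 0.08, censoring them gives Day 28 proportions 1 − [1 − 0.9(1 − exp(−10h))]exp(−18h) = 73.7% vs 88.0%. The truth is 0.9(1 − exp(−28h)) = 67.8% vs 80.4%.

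**The case against.** **The reading is inferred.** A reader might conclude that the plan excludes living non-returners. The documents do not say so. SAP 3.1.4 is qualified as a general rule, the SAP also calls its Kaplan-Meier summary descriptive, and the programming specifications are a separate document not available here. This stands. What is established is that the rule is unstated. Still, where the SAP wants Kaplan-Meier it names it, and the choice changes the result enough to belong in the SAP.

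**The direction is not fixed.** A reader might infer that the summary always shrinks a treatment difference. The calculations do not support that: the mean difference can widen when mortality differs, and a median can reverse with many late returners. With fewer deaths on drug, the mean difference shrank in only 1,061 of 2,000 assumed scenarios.

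**Home oxygen may be captured.** A reader might infer that it is not collected after discharge. Protocol 5.6.3 requires any additional treatment to be recorded as concomitant, and the telephone visits assess concomitant medications. Oxygen is arguably covered; it is simply not named.

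**Other endpoints carry similar information.** Time to grade 6, 7 or 8, the category counts at Days 7 and 28, and the improvement proportions would probably reveal a large recovery difference. That limits the consequence but does not repair this endpoint.

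**Conclusion.** The gap is real and minor. SAP 3.4.1 leaves living non-returners and subjects lost to follow-up without a value or censoring rule. On the likeliest reading, the summary is conditional on recovery or death and can distort the arm comparison.

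Under the assumed rates it usually shrinks the difference in medians. The loss is large when about a quarter or more of an arm has not returned by Day 28 and negligible when nearly all have. Means can move the other way when mortality differs.

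The sizes rest on assumed hazards and death shares, and on deaths being set to 28 days. The effect is confined to one of 13 efficacy endpoints, with no test, p-value or alpha involved.

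**What to change.** In SAP 3.4.1, replace the descriptive summary of this endpoint with Kaplan-Meier or cumulative incidence by treatment group in the ITT Population:

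- Report the median with 95% confidence interval and the cumulative proportion returned by Day 28.
- Keep deaths as non-returners through Day 28. Censor living non-returners at Day 28 or last contact.
- Add a sensitivity analysis that counts subjects of unknown status as not returned, because censoring them may be informative.
- Define return against the SAP 3.3.4 baseline item, "Pre-hospitalization oxygen requirement (None, Low-flow or High-flow Nasal cannula or CPAP mask").
- State one rule for subjects already at that level at baseline, for example leaving them out of the time curve and reporting their number by arm.
- After discharge, use telephone-visit clinical status and concomitant-treatment records. Where home oxygen is not recorded, treat status as unknown.

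The cost is SAP wording and slightly more programming, using a method already planned for the neighbouring endpoint. The drawback is that return dates after discharge will be coarse, since they rest on weekly telephone visits.
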